Effects of SinuSonic on Psychological and Physical Well-Being

NCT number NCT06268730
Document Date 12/26/2023

Effect of the SinuSonic Device on Psychological and Physical Well-Being in Adults with Nasal/Sinus Congestion
PI (UNC): [name]

Brief background: Chronic nasal congestion impacts the functioning of the ventral vagal complex (VVC), which includes cranial nerves of the face and head (special visceral efferents), along with vagal regulation of the heart and lungs. Physiological compromise of the VVC due to a current or previous adverse experience may allow for worsening nasal congestion, which then has a circular impact back to poorer vagal regulation of the lungs.

This chronic cycle of congestion and poor vagal regulation can likewise impact mental health. Defensive symptoms/behaviors, such as anxiety and depression, are common emergent symptoms of a compromised VVC.

Purpose: The first aim of the study is to evaluate relationships between current/previous adverse events, degree of nasal congestion, perception of autonomic regulation and symptoms of anxiety and depression via self-report questionnaires.

The second aim of the study is to evaluate the effect of the SinuSonic on physical and psychological well-being in individuals with chronic nasal congestion. The SinuSonic is a self-applied nasal device designed to enhance physical well-being by reducing nasal congestion via simultaneous administration of acoustic vibration and gentle oscillating expiratory pressure. The vibration and expiratory pressure stimulate several cranial nerves that are included in the ventral vagal complex (VVC), including the cranial nerves of the face and head (special visceral efferents). According to the Polyvagal Theory (Porges, 1995, 1998, 2001, 2003, 2007), when the VVC is stimulated, the functioning of related cranial nerves and emergent behaviors should improve, supporting a calmer, more regulated nervous system, and improved mental health.

To evaluate the effects of the SinuSonic, self-report questionnaires will be administered (via RedCap) prior to beginning use of the SinuSonic, weekly during directed use of the SinuSonic (2 minutes per day, 2 times per day), and after 5 weeks of use of the SinuSonic. Weekly self-report questionnaires will include amount of SinuSonic usage and degree of nasal congestion. The final, 5-week questionnaires will include degree of nasal congestion, perception of autonomic regulation and symptoms of anxiety and depression.

As this is a feasibility/pilot study, data from the study will be used to estimate effect sizes and inform a larger, randomized trial on the effects of the SinuSonic on individuals with compromised autonomic regulation, if warranted by the results.

Background: The SinuSonic was developed as a non-pharmaceutical device aimed to reduce nasal congestion via simultaneous administration of acoustic vibration and gentle oscillating expiratory pressure. Previous studies have demonstrated significant improvements in congestion and ease of breathing after immediate use of the device (Cairns & Bogan, 2019) and after twice daily use for 5-weeks (Soler et al., 2020). In this study, there was significant improvement in peak nasal inspiratory flow after only 2 weeks of use, and significant improvement in multiple self-report measures of congestion after 5 weeks of use. No adverse effects were reported. A review report by Schlosser, Salley and Soler likewise concluded that the device may improve pregnancy-related rhinitis, which may be particularly important for individuals who would prefer non-pharmacological interventions while pregnant or breastfeeding (<https://sinusonic.com/blogs/learn/pregnancy-rhinitis.>)

[figure not shown]
There are common clinical symptoms, such as anxiety and depression, that are frequently associated in individuals who feel unhealthy. The Polyvagal Theory (Porges, 1995, 1998, 2001, 2003, 2007) provides a model for which these psychological and physical symptoms may be viewed as the predictable consequences of a common neural substrate. This neural substrate involves the neural regulation of the heart and lungs, as well as neural regulation of the muscles of the face and head which function together as a Ventral Vagal Complex (VVC).

The VVC is based on the documented neuroanatomical and neurophysiological pathways between the brainstem areas that regulate the muscles of the face (via special visceral efferent pathways) and the heart and lungs (via the vagus). Features of the VVC may serve as a clinical checklist converging on symptoms of anxiety and depression as observed in several clinical disorders including autism (Bal et al., 2010; Patriquin et al., 2011; Porges et al., 2012; Van Hecke et al., 2009), Fragile-X-Syndrome (Heilman et al., 2011), selective mutism (Heilman et al., 2012), prematurity (Doussard-Roosevelt, et al., 1997), prenatal exposure to opiates and alcohol (Suess et al. 1997), PTSD (Sahar et al., 2001), perpetrators of domestic abuse (Umhau et al., 2002), Borderline Personality Disorder (Austin et al., 2007), behavioral regulation problems (Dale et al., 2011), and abuse and neglect (Dale et al., 2009). However, relating symptoms of anxiety and depression to an illness that impacts the functioning of the VVC (i.e., nasal congestion impacts the functioning of the vagus at the lungs) is a novel aspect of the current study.

Additionally, individuals who already have a compromised VVC due to adverse events (history or current), may also be at risk for the continued cycle of VVC complications (i.e., chronic congestion, anxiety and/or depression).

In summary, the function of the SinuSonic (i.e., reducing nasal congestion while improving vagal regulation of the lungs) align with the theoretical principles of the Polyvagal Theory. Thus, our proposed research will serve to determine whether the SinuSonic will have a significant impact on the reduction and management of physical and psychological symptoms (i.e., anxiety and depression), as they are described within the context of a dysregulated VVC.

Flowchart of Research Procedures:

Participants

50 adults (aged 18-99 years) with self-reported nasal congestion will be recruited for the study. Participants must be US residents.

Data Collection Procedures

Step 1: Recruit/Eligibility Screening

Individuals who make a purchase of the SinuSonic device will receive a recruitment flyer in the shipping box for their device, but only new users of the SinuSonic will be eligible to participate. The recruitment flyer will contain a QR code that users can scan to access the Eligibility Screening for the study in RedCap. Staff at SinuSonic has agreed to include the recruitment flyer when shipping packages.

The Eligibility Screening will consist of the following questions:

- 1) Are you between ages 18-99 years old? [YES TO QUALIFY]
- 2) Have you ever used the SinuSonic device? [NO TO QUALIFY]
- 3) Do you meet any of the conditions listed under the Safety and Warnings for use of the SinuSonic device? [NO TO QUALIFY]
 - a) Current or history of breathing problems (i.e., asthma, chronic obstructive pulmonary disorder (COPD), chronic bronchitis, emphysema, pneumonia, pleural effusion, lung cancer, cancer of the throat or upper airway)

- b) Current or history of circulatory problems (i.e., active nose bleed, heart arrhythmia, coronary artery disease, congestive heart failure, heart attack)
- c) Other conditions, specified as brain tumor, moderate to severe ear pain, fever greater than 101 degrees

- 4) Have you experienced symptoms of nasal congestion that have persisted at least 2 weeks? [YES TO QUALIFY]
- 5) Is your current level of nasal congestion at 5 or higher? (VAS included here) [YES TO QUALIFY]

Step 2: Consent/Linkage File

When all eligibility criteria are met, individuals will be invited to access the Informed Consent document (also provided via RedCap) to read and e-sign. Phone number and email address for the researcher will be provided in the event of questions or request for clarification.

After receiving the e-signed informed consent, researchers will assign a SubjectID number so that the participant can use the SubjectID number when completing all questionnaire assessment sessions using RedCap. Researchers will maintain a database linking SubjectID and name on their password-protected computers that will not be accessible to anyone who is not affiliated with the research.

Step 3: Pre-SinuSonic assessment

Participants will be asked to complete this assessment, via RedCap, prior to beginning use of the SinuSonic. Researchers will provide participants with a link to the assessment (text or email), along with their unique SubjectID number to use. The following instruments will be programmed into RedCap for completion:

Prior to SinuSonic Use (week 0):

- 1) Demographic Information Form
- 2) SF12 to assess overall health ("how you feel and how well you are able to do your usual activities")
- 3) TNSS to assess current nasal symptoms
- 4) BPQ to reflect perception of autonomic regulation
- 5) HADS to assess anxiety and depression
- 6) ATES to assess history of trauma/adverse events

Step 4: SinuSonic Use / Weekly assessments

After completing the pre-SinuSonic assessment, researchers will inform participants to begin directed use of the SinuSonic (2 minutes per day, 2 times per day). Participants will be asked to confirm SinuSonic use on a weekly questionnaire. Additionally, participants will be asked to complete the following questionnaires approximately 5 minutes after final SinuSonic use for that week. The following instruments will be programmed into RedCap for completion:

Weekly, for 4 weeks (end of week 1, 2, 3, 4).

- 1) TNSS to assess current nasal symptoms
- 2) PGIC to reflect change in activity limitations, symptoms, emotions and overall quality of life

Step 5: Final research assessment

Participants will be asked to confirm use of the SinuSonic on a weekly questionnaire. Additionally, participants will be asked to complete the following questionnaires approximately 5 minutes after final SinuSonic use on the 5th consecutive week. The following instruments will be programmed into RedCap for completion:

End of Study (end of week 5).

- 1) TNSS to assess current nasal symptoms
- 2) PGIC to reflect change in activity limitations, symptoms, emotions and overall quality of life
- 3) BPQ to reflect perception of autonomic regulation
- 4) HADS to assess anxiety and depression

Description of Measures

Body Perception Questionnaire (BPQ) (Cabrera et al., 2018). The Body Perception Questionnaire (BPQ) is a self-report measure of body awareness and autonomic reactivity. Its items are based on the organization of the autonomic nervous system (ANS), a set of neural pathways connecting the brain and body. These pathways send information from the body about the status of organs and tissues (i.e., afferent projections). Some of these incoming signals form a basis for the subjective awareness of the body. The ANS also carries signals that control the functions of these organs and tissues (i.e., efferent projections). These signals can alter the functions of the body, depending on internal and external needs. Only the Autonomic Reactivity subscale will be distributed and used for the current study.

Hospital Anxiety and Depression Scale (HADS) (Zigmond & Snaith, 1983). HADS is a fourteen-item scale with seven items each for anxiety and depression subscales. Scoring for each item ranges from zero to three. A subscale score >8 denotes anxiety or depression.

Short-Form Health Survey-12 (Ware et al., 1995). The SF-12 is a health-related quality-of-life questionnaire consisting of twelve questions that measure eight health domains to assess physical and mental health. Physical health-related domains include General Health (GH), Physical Functioning (PF), Role Physical (RP), and Body Pain (BP)

Total Nasal Symptom Score. The Total Nasal Symptom Score (TNSS) is the sum of scores for each of nasal congestion, sneezing, nasal itching, and rhinorrhea at each time point, using a four point scale (0–3), where 0 indicates no symptoms, a score of 1 for mild symptoms that are easily tolerable, 2 for awareness of symptoms which are bothersome but tolerable and 3 is reserved for severe symptoms that are hard to tolerate and interfere with daily activity. TNSS is calculated by adding the score for each of the symptoms to a total out of 12.

Adverse Traumatic Experiences Scale (ATES) (Kolacz et al., 2020). This measure asks about childhood adverse experiences, childhood maltreatment, other person maltreatment, life-threatening situations, sudden deaths of close ones, and personal health situations. Respondent-reported prior adverse events

of maltreatment, life-threatening situations, and sudden deaths of close ones are summed to create an adversity score (range: 0–19).

Patient Global Impression of Change (PGIC) (Hurst & Bolten (2004). The self-report measure Patient Global Impression of Change (PGIC) reflects a patient's belief about the efficacy of treatment. PGIC is a 7 point scale depicting a patient's rating of overall improvement. Patients rate their change as "very much improved," "much improved," "minimally improved," "no change," "minimally worse," "much worse," or "very much worse."

Data Analyses

Questionnaire data will be entered by participants into RedCap for researcher access. Researchers will export the data into SPSS for data analyses. All databases will be stored on password protected computers, accessible only to researchers affiliated with the study, and backed up on UNC servers.

As the current proposal is for a feasibility/pilot study, researchers will evaluate the following aims to determine whether a larger, randomized trial is warranted.

Aim 1: Examine associations between nasal congestion, autonomic functioning, adverse events, and mental health indices (depression, anxiety) at baseline. Pearson correlation analyses will be used to evaluate relationships among measures at each timepoint.

Aim 2: (*These would be the aims for a future, randomized clinical trial, with preliminary testing using data from the current feasibility/pilot study*): Evaluate the effect of the SinuSonic on users with chronic nasal congestion. We will focus on three constructs important to psychological and physical health and hypothesize that:

- A) Nasal congestion will significantly improve when comparing baseline measures to follow-up measures at each week, and will maintain effects at 5 weeks. Repeated measures ANOVA will be used to evaluate mean change in outcome measures across time in PGIC and TNSS.
- B) Autonomic functioning will significantly improve when comparing baseline measures to end of study. Repeated measures ANOVA will be used to evaluate mean change in BPQ across time.
- C) Mental health indices (depression, anxiety) will significantly improve when comparing baseline measures to end of study. Repeated measures ANOVA will be used to evaluate mean change in HADS across time.

Aim 3: (*This would be an aim for a future, randomized clinical trial, with preliminary testing using data from the current feasibility/pilot study*). Evaluate the mediating effect of current/previous adverse experiences on outcome measures at 5 weeks, using regression models.

Aim 4: Calculate effect sizes for each outcome variable, which will be necessary to determine adequate sample size for a future clinical trial. G-Power software will be used to determine sample sizes based on the effect sizes of the current outcome measures.

References

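### The protocol says the study will determine the device's impact, but a one-group before-after study of new purchasers can only estimate change during use

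*Combined protocol and SAP*

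**What the plan says.** Two statements of purpose use causal language without a limit in the sentence itself.

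- Background, closing summary paragraph: "our proposed research will serve to determine whether the SinuSonic will have a significant impact on the reduction and management" of symptoms, with anxiety and depression named.
- Purpose: "The second aim of the study is to evaluate the effect of the SinuSonic on physical and psychological well-being" in people with chronic nasal congestion.

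The design is described as follows.

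- Participants: "50 adults (aged 18-99 years) with self-reported nasal congestion will be recruited for the study".
- Step 1 (recruitment): "Individuals who make a purchase of the SinuSonic device will receive a recruitment flyer in the shipping box for their device". Only people who have never used the device qualify.
- Eligibility Screening: item 4 asks for symptoms lasting at least 2 weeks. Item 5 asks "Is your current level of nasal congestion at 5 or higher" on a visual analogue scale (VAS), and a yes is needed to qualify.
- Steps 3 to 5: everyone completes a week-0 assessment, is then told to begin use, and is followed by self-report questionnaire to week 5. No control group, sham, randomization or blinding is described.
- Data Analyses, Aim 2 A to C: repeated measures ANOVA over time within the one group, with the hypothesis that each construct will improve significantly.

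Other text is more modest. The paragraph that follows the Purpose calls this a feasibility/pilot study that will estimate effect sizes for a larger randomized trial. The Data Analyses section says the aims serve to decide whether such a trial is warranted. Aim 2, "Evaluate the effect of the SinuSonic on users with chronic nasal congestion", is introduced by an italic label that assigns it to a future randomized trial, with preliminary testing in this one.

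**The concern.** To determine whether a device has an impact, one must compare what happened with what would have happened without it. This study has no source for the second quantity. Each participant's own baseline stands in for it, which is adequate only if nothing but the device could move the scores over 5 weeks.

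The protocol's own entry and recruitment rules make that unlikely. People enter when congestion is at or above a threshold, may have had it for as little as 2 weeks, and have bought the product whose benefit they then rate.

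What is at stake is the conclusion. Under the Background sentence as written, a significant fall in nasal symptom, anxiety or depression scores would answer the stated question in the device's favour. Under the pilot wording, the same result would only help to plan a randomized trial. The protocol should hold one of these positions throughout.

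**Working it through.** **Claim against design.** The documents give no alpha, power, effect size, standard deviation or dropout rate, so there is no planned figure to reproduce. The main check is to set the claim beside the design.

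| Needed to attribute change to the device | What the protocol provides |
|---|---|
| A concurrent comparison group | None described; all are told to use the device |
| Protection against expectation | None described; all bought the device and all outcomes are self-reported |
| Stable symptoms, or an untreated course to compare with | At least 2 weeks of symptoms; no untreated follow-up |
| Entry that does not favour later improvement | Threshold of 5 or higher on current congestion |

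Single-arm and unblinded are inferences from the procedures; the protocol does not use those words, and nothing in it points the other way. An ANOVA on time tests whether the mean changed. It cannot say why.

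**How much could regression to the mean contribute?** This is an illustration under assumed inputs, for the Total Nasal Symptom Score (TNSS), with no device effect. Selection is on the screening VAS, whereas baseline is a separate TNSS taken after consent. Assume normal scores in SD units and let:

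- c = entry cut-off relative to the mean of the source population, and λ = φ(c)/(1 − Φ(c));
- r0 and r5 = correlation of the screening score with week-0 and week-5 TNSS;
- r05 = correlation of week-0 with week-5 TNSS.

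Then:

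- expected fall = (r0 − r5) × λ;
- SD of change = √[2(1 − r05) − (r0 − r5)² × λ(λ − c)];
- dz = fall / SD of change.

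The chance of a significant improvement comes from a paired t-test with n = 50 and two-sided 0.05, counting the favourable direction only (nominal 2.5%).

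| c | r0, r5, r05 | Fall (SD) | dz | Chance of significant improvement |
|---|---|---|---|---|
| any | r0 = r5 | 0 | 0 | 2.5% |
| −0.5 | 0.7, 0.6, 0.6 | 0.1 × 0.509 = 0.051 | 0.06 | 6% |
| 0 | 0.7, 0.6, 0.5 | 0.1 × 0.798 = 0.080 | 0.08 | 8% |
| 0 | 0.7, 0.6, 0.6 | 0.1 × 0.798 = 0.080 | 0.09 | 9% |
| 0 | 0.7, 0.4, 0.5 | 0.3 × 0.798 = 0.239 | 0.25 | 40% |
| 1 | 0.7, 0.4, 0.5 | 0.3 × 1.525 = 0.458 | 0.48 | 91% |

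For the fourth row, SD of change = √[0.8 − 0.01 × 0.637] = 0.891, and 0.080/0.891 = 0.09.

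The range runs from no inflation to near-certain false significance, and the documents do not say where this study lies in it. Natural course, expectation and selective dropout are not in the calculation. The autonomic (BPQ) and anxiety/depression (HADS) scores are not selection criteria, so the table says little about Aims 2B and 2C.

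**The case against.** The strongest reply is that the protocol already knows this. It calls itself a feasibility/pilot study, uses its results to plan a randomized trial, and labels Aim 2 as that trial's aim with only preliminary testing here. A single-group pilot is a legitimate choice, and no stated decision requires change to be credited to the device.

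Most of this stands, and it limits the point to wording. It does not remove the point. The Background sentence carries no such limit, and the Purpose aim is qualified only by the pilot statement that follows it. *Preliminary* describes how strong the evidence is, not what it is evidence of: an uncontrolled preliminary test is still uncontrolled. No sentence says that change will not be attributed to the device.

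A reader might infer three stronger things that the documents do not support.

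- *That Aim 2 is an unqualified test of efficacy.* Its own label says otherwise, although hypotheses A to C still speak of significant improvement.
- *That regression to the mean alone will probably produce a significant result.* Baseline TNSS is measured after screening, on a different instrument. If the screening score is equally correlated with week-0 and week-5 TNSS, the expected fall is zero.
- *That a causal claim will be published.* The protocol does not say how results will be reported.

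**Conclusion.** The point holds as an overstatement in two sentences of purpose. A one-group before-after study of 50 new purchasers with self-reported outcomes can estimate how scores change over 5 weeks of use. It cannot determine whether the device caused the change.

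This rests on the design as described and on no numerical assumption. The size of the possible bias is unknown: for TNSS, regression to the mean alone could add nothing or a great deal, depending on correlations and a cut-off position that the documents do not give.

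The severity is modest because the pilot framing and the Aim 2 label already point the right way. It is still worth correcting, because the protocol is inconsistent about what its result will mean and the change alters what can be concluded.

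**What to change.** 1. Reword the closing Background sentence and the second aim in the Purpose to say that the study will *estimate within-person change over 5 weeks of use in new purchasers, to inform a randomized trial*.
2. Report Aim 2 A to C as mean change from baseline with a 95% confidence interval where a baseline exists, which means TNSS, BPQ and HADS. The global impression of change (PGIC) is first collected at the end of week 1 and has no baseline, so it cannot be handled this way. With 50 completers the interval half-width is 2.010/√50 = 0.28 SD of the change score; with 40 it is 0.32.
3. Add one sentence to Data Analyses stating that change will not be attributed to the device without a control group.

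No procedure, sample size or data collection has to change. The cost is a less favourable stated claim.

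Adding the TNSS items to the screening survey, to show drift before use, is not recommended. Screening comes before consent and before SubjectID assignment, and the gap to week 0 is unspecified. It could not show five weeks of natural course or any expectation effect once use begins.

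### Participants hold the device before screening, and nothing described in the plan checks for use between screening and the week-0 baseline

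*Combined protocol and SAP*

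**What the plan says.** In the combined protocol and SAP, Step 1 (Recruit/Eligibility Screening) sets the recruitment route: "Individuals who make a purchase of the SinuSonic device will receive a recruitment flyer in the shipping box for their device". The flyer leads to remote self-screening: "The recruitment flyer will contain a QR code that users can scan to access the Eligibility Screening for the study in RedCap". The same paragraph limits entry: "only new users of the SinuSonic will be eligible to participate". Question 2 of the Eligibility Screening applies that limit by self-report: "Have you ever used the SinuSonic device"; a no is needed to qualify.

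Step 2 (Consent/Linkage File) then places e-consent and a staff action before baseline: "After receiving the e-signed informed consent, researchers will assign a SubjectID number". In Step 3 (Pre-SinuSonic assessment) researchers send a link by text or email, and the timing of the baseline is put as a request: "Participants will be asked to complete this assessment, via RedCap, prior to beginning use of the SinuSonic". Step 3 lists six week-0 instruments: a demographic form, SF12, TNSS, BPQ, HADS and ATES.

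Step 4 (SinuSonic Use / Weekly assessments) has researchers tell participants to begin directed use once week 0 is complete. From then on, use is confirmed on weekly questionnaires.

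**The concern.** Everyone recruited by this route has the device in hand from before screening until week 0. They bought it for congestion and, to qualify, must rate current congestion at 5 or higher and report at least two weeks of symptoms. They have both the means and a reason to try it early. If some do, their week-0 values are not pre-use values, and the researchers would have no record of it.

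The baseline carries much of the analysis. The study has no control arm, so week 0 is the only reference for change in TNSS, BPQ and HADS under Aim 2. Aim 1 correlates the baseline measures. Aim 4 passes the effect sizes to a sample-size calculation for a future trial. A TNSS baseline lowered by early use would understate the change and make that future trial look larger than it needs to be.

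**Working it through.** The plan gives no effect size, standard deviation, rate of early use or derivation of its 50 participants, so there is no figure to reproduce. The check is a trace of the order of events, followed by an illustration on assumed inputs.

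**Order of events**

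| Point in the study | What the plan provides on device use |
|---|---|
| Device delivered with flyer (Step 1) | Nothing recorded |
| Screening (question 2) | One self-reported yes/no item on any prior use |
| E-consent, SubjectID, link sent (Steps 2-3) | Nothing recorded; no maximum interval stated |
| Week 0 (Step 3) | Request to complete before use; no listed instrument asks about use since screening |
| Start of directed use (Step 4) | Researchers tell participants to begin, after week 0 |
| Ends of weeks 1-5 (Steps 4-5) | Use confirmed weekly; not described as reaching back before week 0 |

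The unrecorded window runs from the screening answer to the week-0 survey. The plan mentions no date of first use and no rule for analysing someone who started early.

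**Which outcomes are exposed**

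- *TNSS*: the Background cites improvement in congestion and ease of breathing after immediate use. Follow-up TNSS is taken about five minutes after the week's last session, so the intended contrast is unexposed against just-used. For a participant who used the device shortly before week 0, both ends are post-use and any acute part of the effect drops out.
- *BPQ and HADS*: their change also rests on week 0, but the documents give no evidence of an immediate effect on either.
- *PGIC*: first collected at the end of week 1, so it has no week-0 value to contaminate.

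**Illustration (all inputs assumed)**

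Let f be the share who start early and g the share of the device effect they already have at week 0. Suppose early starters reach the same follow-up level as the others and the standard deviation is unchanged. Then:

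observed change = true change × (1 − f × g)

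With an assumed true change of 0.40 SD:

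| f | g | 1 − f × g | Observed change | Sample-size factor 1/(1 − f × g)² |
|---|---|---|---|---|
| 0.10 | 0.5 | 0.95 | 0.38 SD | 1.11 |
| 0.20 | 0.5 | 0.90 | 0.36 SD | 1.23 |
| 0.10 | 1.0 | 0.90 | 0.36 SD | 1.23 |
| 0.20 | 1.0 | 0.80 | 0.32 SD | 1.56 |

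The last column applies because the required sample size varies with the inverse square of the standardised effect. The rows with g = 1 are the upper end: they assume that early starters have the whole effect by week 0.

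As to how many early starters to expect, an assumed 5% chance per participant gives 50 × 0.05 = 2.5 on average, and a probability of at least one of 1 − 0.95^50 = 0.92.

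**The case against.** The strongest reply is that the plan already protects the baseline in four ways: a new-user criterion, a screening exclusion, a request to complete week 0 before use, and a start instruction issued by researchers after week 0. That stands. A reader might infer that the protocol neglects a pre-use baseline, and the text does not support this. The gap is in verification, not in instruction.

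Three other strong readings also fail.

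- *All Aim 2 comparisons are affected.* They are not. PGIC has no week-0 value, and the cited immediate effect concerns nasal symptoms only.
- *Early use could never be detected.* Participants know what they did and stay in weekly contact, so they could be asked. The supportable statement is that the plan describes no way of detecting it.
- *Early starters would lose their whole effect.* The Background describes separate results at two and five weeks and does not say how long the effect of one session lasts, so a partial effect is at least as plausible.

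It can also be said that the contents of the demographic form and the weekly use questionnaire are not shown, so a question on early use may exist there. That cannot be excluded, but none is described. Nothing in the documents shows that early use is common, and the expected bias is toward zero, so it would not create a false benefit. Both points limit the weight of the concern without removing it.

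**Conclusion.** The point holds as a minor, inexpensive improvement. Participants have the device before screening, prior use is asked once, and no described item covers the interval up to week 0. If the device acts as the Background says, early use would lower baseline TNSS and bias the TNSS change and its Aim 4 effect size toward zero. For BPQ and HADS the exposure is structural only.

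The size cannot be determined from the documents. The illustrated loss of 5% to 20% of the change rests wholly on assumed values for the share starting early (10-20%) and the share of the effect already present (half to all). If nobody starts early, there is no bias. The matter should still be settled now, because analysts cannot recover use data that were never collected.

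**What to change.** Add one item at the start of the week-0 RedCap survey: *Have you used the device since the screening questions? If yes, how many times and when last?* Keep participants who answer yes and flag them. Specify in Data Analyses that the TNSS, BPQ and HADS changes and the Aim 4 effect sizes will be reported with and without the flagged participants.

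The cost is one survey item and one sensitivity analysis; recruitment and eligibility do not change. The item is again self-report, and someone who did not follow the request may not say so, so it reduces the gap without closing it. With 50 participants the comparison may turn on very few people and should be presented as descriptive. If nobody reports early use, the item still documents that no one reported a contaminated baseline, which is useful in a feasibility study.
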